1. SYNOPSIS

Study Title	Does surgery for asymptomatic carotid stenosis reduce the long-term risk of dementia, stroke, death and other important health outcomes? Extended UK post-trial follow-up of the first Asymptomatic Carotid Surgery Trial (ACST-1). Phase 2	
Internal ref. no. / short title	ACST-1 follow-up study of memory and thinking function	
Study Design	This Protocol outlines use of short IQCODE for surviving ACST-1 UK participants who would be contacted for consent to implement the short IQCODE dementia screening questionnaire to be completed by an 'informant' such as a relative or friend of the participant. The results of the IQCODE questionnaire is to supplement extended long-term follow-up through electronic data linkage of National health records for 1601 UK & Swedish ACST-1 participants that has already been completed with analysis ongoing.	
Study Participants	UK participants of ACST-1	
Planned Sample Size	~230 surviving participants of ACST-1	
Planned period of research	2019- 2020	
Qualitative study phase	Objectives	Outcome Measures
	
To provide current cognition information in surviving ACST-1 UK participants to add to the information on dementia provided through the completed data linkage part of the study.
 
The overall study (data linkage and IQCODE) may determine whether carotid endarterectomy reduces the long-term risk of dementia.
	
Single assessment by telephone via the short form of the Informant Questionnaire on Cognitive Decline in the Elderly (IQCODE). This is a validated screening assessment questionnaire for dementia completed by a relative or friend (informant) considering any change in cognition from 10 years to date of assessment in the surviving participant

2. ABBREVIATIONS

ACST-1	First Asymptomatic Carotid Surgery Trial
CAG	Confidentiality Advisory Group
CEA	Carotid endarterectomy
CI	Chief Investigator
CMT	Contemporary Medical Treatment
CTRG	Clinical Trials & Research Governance, University of Oxford
GCP	Good Clinical Practice
GP	General Practitioner
HES	Hospital Episode Statistics
HR	Hazard ratio
HRA	Health Research Authority
IQCODE	Informant Questionnaire on Cognitive Decline in the Elderly (short form)
K-M	Kaplan Meier
NHS	National Health Service
IQR	Interquartile Range
REC	Research Ethics Committee
SCR	Summary Care Records
SOP	Standard Operating Procedure

Dementia is an insidious condition that develops over many years. Therefore, long-term follow-up is necessary to determine the effect of carotid endarterectomy on cognitive decline or dementia. Although new trials of carotid endarterectomy versus contemporary medical management [e.g. 2nd European Carotid Surgery Trial www.ecst-2.com and CREST-2 <http://www.crest2trial.org/>] may provide answers to this question in the future, it will take many years and for definitive results to emerge. There are no long-term reports of cognitive impairment or dementia from randomised trials of carotid artery stenting or endarterectomy. Therefore, long-term follow-up of a large randomised trial is an appealing method to determine the effect of carotid intervention on later dementia.

Participants were eligible for ACST-1 if: (1) they had severe unilateral or bilateral carotid artery stenosis (generally carotid artery diameter reduction at least 60%, although there was no fixed minimum

percentage); (2) this stenosis had not caused stroke, transient cerebral ischaemia, or any other relevant neurological symptoms in the 6 months before recruitment; (3) no circumstance or condition precluded long-term follow-up; and (4) doctor and participant were both substantially uncertain whether to choose immediate CEA or deferral of any CEA until it seemed needed (e.g. if symptoms occurred).

Phase 1 of the study is now complete (Phase 1 protocol: ethics 16/SC/0406) and CAG (16/CAG/0122) approval for data linkage with National electronic health records held by NHS Digital in England and similar bodies in Scotland, Northern Ireland and Socialstyrelsen in Sweden) is now complete. See study flow chart (Appendix A).

Whilst linked data is a very important resource for the detection of dementia after carotid endarterectomy, it is likely that these datasets under ascertain dementia. Therefore it very important that we use overlapping methods to maximise ascertainment of dementia and significant cognitive impairment. Therefore for this part of the study we propose to follow-up 230 surviving UK participants allocated to carotid endarterectomy or control from the Asymptomatic Carotid Surgery Trial, ISRCTN26156392, (start date 01/04/1993: end date 31/12/2008)¹², measuring rates of dementia or cognitive impairment in those allocated to either CEA plus contemporary medical treatment or to contemporary medical treatment (CMT) alone.

This protocol is the final part of the research where we propose to complement the electronic data linkage already undertaken for dementia diagnosis with information from the short IQCODE questionnaire for UK survivors in ACST-1.

Our proposed research is therefore an important part of testing the hypothesis that, by undertaking CEA, cerebral embolization from carotid atheroma may be prevented, reducing later risk of dementia.

Patient numbers and the long follow-up in ASCT-1 may be sufficient to enable us to detect an effect of carotid intervention on dementia more reliably than any previous study. If a reduced risk of dementia is demonstrated in addition to the known reduction in subsequent stroke for participants who had endarterectomy, this would alter the perceived benefits and harms of surgery, and help future decision making for patients with carotid stenosis.

4. OBJECTIVES AND OUTCOME MEASURES FOR PHASE 2

Objectives	Outcome Measures	Timepoint(s) of evaluation of this outcome measure

Primary Objective: To provide current cognition information in surviving ACST-1 UK participants to add to the information on dementia provided through the completed data linkage part of the study.
 
The overall study may determine whether carotid endarterectomy reduces the long-term risk of dementia.
	
A cognitive impairment score to inform diagnosis of dementia and complementing data linkage with electronic health records
	
Single assessment by telephone via the short form of the Informant Questionnaire on Cognitive Decline in the Elderly (IQCODE). This is a validated screening assessment questionnaire for dementia by completed by a relative or friend (informant) determining changes in cognition from 10 years to the date of the assessment in the surviving participant. To be implemented Spring- 2019.

TABLE 1 Primary Objective and outcomes of the study: Phase 2

5. STUDY DESIGN

Long-term follow-up of participants from a randomised trial, ACST-1, which randomly allocated 3120 asymptomatic participants from 126 centres in 30 countries, by blinded minimised randomisation, to immediate CEA (median delay 1 month, IQR 0.3–2.5) or CMT with deferral of any carotid procedure. To provide current cognition information in surviving ACST-2 UK participants to complement the dementia information already provided through the data linkage that has already been completed.

For this final part of the study we will contact UK surviving participants (informed through data linkage with all-cause mortality electronic) for permission to undertake the single assessment short IQCODE screening informant questionnaire for the potential diagnosis of dementia (see section 7.2 for further details). Objective measurement of any cognitive decline from the short IQCODE questionnaire results will augment and complement dementia diagnoses from the electronic data linkage.

6. PARTICIPANT IDENTIFICATION

6.1. Study Participants

All surviving participants randomised in ACST-1 in the UK will be sent an invitation to participate in this follow-up by asking an informant (relative or friend of the participant) to complete a telephone questionnaire.

6.2. Inclusion Criteria

Randomisation of participants in ACST-1 was performed via Clinical Trial Service Unit (CTSU), University of Oxford with participant details and data stored securely at CTSU.

Inclusion criteria:

1. ACST-1 participant
2. Resident in UK
3. Known to be alive in March 2019
4. Consented to take part and nominated a relative or friend to complete the IQCODE questionnaire

Exclusion Criteria:

None

7. STUDY PROCEDURES

Participants' details from ACST-1 have been retained securely by University of Oxford as per Section 33 of the Data Protection Act (1998). This includes identifiable participant information, at the time of consent for ACST-1 and participant contact details updated if appropriate during the trial.

The Chief Investigator of ACST-1 will ensure that all data protection laws and their approval bodies in the UK will be adhered to as the data processor and that the secure copies of approvals will be made and stored in University of Oxford as data controller.

7.1. Implementation of Short IQCODE screening questionnaire for dementia

1. We will determine first which UK participants are known to be alive with linkage to mortality data already received (this is about 230 of 1069 original UK participants). As this is an elderly cohort, a second check for vital status will be made immediately prior to contact through the NHS Spine - NHS Summary Care Records (SCR).
2. We will also obtain up-to-date address from the NHS Summary Care Record. We will seek permission for access to the NHS Summary Care Record from the HRA Confidentiality Advisory Group (CAG) under the precedent set criteria, category 7, 'validity of consent' where contact details are held with consent but up-to-date details are required.
3. We will initially contact surviving UK participants by post. The mailing will include an invitation to take part with a participant information sheet, consent form and prepaid reply envelope. We would ask for the participant to consent to the proposed follow-up and for their named 'informant' (a relative or friend) to consent to be contacted by telephone to complete the IQCODE questionnaire. A prepaid address envelope will be provided for return of the consent form.

4. As sensitive information will be sent through the post e.g. name, address and participation in a trial, the mail out will be sent to the ACST-1 participant by recorded delivery marked 'private and confidential' as per University of Oxford guidelines. We will make every effort to contact the participants e.g. contacting a nursing home or hospital if they are found to be resident there. When the signed consent form is received in the ACST trials office the study coordinator (registered nurse) would then contact the participant's nominated relative or friend, 'the informant', to complete with them the short IQCODE questionnaire over the telephone.
5. There will also be a dedicated contact telephone number for participants, the relative or friend, to contact the study coordinator (or the ACST research team in her absence) during office hours to answer any queries or concerns.

As part of the informed consent, we have also included information on memory loss:

<https://www.alzheimers.org.uk/get-support/publications-and-factsheets/worried-about-your-memory>

<https://www.nhs.uk/conditions/dementia/worried-someone-has-dementia/>

6. A copy of the consent form would be made and sent back to the participant.
7. The participant will be informed that taking part is entirely voluntary and they can withdraw from the study at any time. There will also be an option on the consent form for the participant to actively decline to take part in this follow-up and to send this back in the prepaid envelope provided. They would then be removed from the follow-up IQCODE study database and they would not be contacted again.
8. If there is no response from a participant within 3 weeks after the initial mailing, we will resend the invitation to participate one more time. We will check participants' vital status and address again immediately prior to the posting out of the reminders in case there has been a change since the initial mailing. The reminder letters will also be sent recorded delivery and marked 'private and confidential'.
9. For non-responders to both mailings we will not follow-up further.
10. Data entry of short IQCODE scores into the study database.

See Study Flow Chart (Appendix A)

7.2. Patient & Public Involvement (PPI)

We have sought Public and Patient Involvement (PPI) panels for the study through the Alzheimer's Society Research Network Volunteers (people living with dementia as relatives, friends or carers) and the Nuffield Department of Population Health (NDPH) Public Panel (eight members).

The study has two Alzheimer's Society Research Network Volunteers who are working with us for the duration of the project. We have incorporated their feedback into our design and methodology.

We have also received excellent PPI feedback through the successful application process for an Alzheimer's Society grant (see supporting documents).

The long-term follow-up of ACST-1 has also a web page devoted to the purpose and methodology of the study for lay readers with links to and from the Alzheimer's Society website.

<https://acst-2.org/acst1.html>

PPI responses were overwhelmingly positive and there were no concerns with the study design.

We are re-contacting participants after a time lapse of up to 10-years but this is an engaged cohort that previously has completed annual questionnaires for up to 15 years. In addition, at present, there is no other randomised cohort of patients who have had treatment of carotid stenosis where extended long-term follow-up is possible to assess the risk of dementia. Prevention of dementia is a current health priority and a new trial would be extremely expensive whilst not making best use of existing information.

7.3. Consent

Participants have already consented to long-term follow-up. At the time of recruitment into ACST-1, participants consented to allow access to their medical records by the trial team on a long-term basis. Neither the consent form, nor the participant information leaflet put a time limit on the last time that medical records would be inspected (for evaluating the trial intervention).

For this study as part of the long-term follow-up, we will ask surviving UK ACST-1 participants, and their nominated informant (a relative or friend) to sign a consent form to take part, including telephone contact details and return it to the coordinating centre using the prepaid envelope provided. We would assume capacity to understand what is intended in the study from return of the completed consent form, however this will also be determined by telephone contact with the informant. If there is any doubt over capacity we would not proceed with the questionnaire follow-up.

There is included on the consent form a yes/no option for participation so if they wish they can actively opt-out of this follow-up by selecting 'no' and returning in the prepaid envelope provided. They would not then in this instance be sent a reminder and would be removed from the IQCODE study database.

Some participants will not, for whatever reason, be able to consent or name an informant. Most would likely in this case to be non-responders to the initial and reminder mailing and their name would be removed from the IQCODE study database, although their data would be kept for the followup into electronic health records.

In some instances it may be that, a relative might contact the study coordinator, having seen the study documents, and if applicable the coordinator may ask for and record any dementia, type (if known) and date of diagnosis of the ACST-1 participant.

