9. STATISTICS AND ANALYSIS

9.1. The Number of Participants

Between 1993 and 2003, the ACST-1 trial included 3120 participants from 30 countries (n=1601 from UK and Sweden). Asymptomatic patients with substantial carotid stenosis, considered suitable for surgery were randomly allocated to a policy of immediate carotid endarterectomy plus contemporary medical management versus contemporary medical management alone. Of those allocated immediate endarterectomy, 90% had the procedure within 1 year after randomisation (92% by 10 years); of those

allocated to deferral, 7.5% had the procedure in the first year within the first year (34% by 10 years – as substantial numbers had developed symptoms during follow-up).

The median age of participants recruited to ACST-1 was 69 years, and 34% were women. The mean age of UK surviving participants is now 81 yrs. At the time of the last trial report (2010) median follow-up to 2008 was around 9 years (IQR 7-17 years) but with this study we would achieve an additional 10 years of follow-up.

For the short IQCODE questionnaire, the data linkage with UK National health records (n=1069) suggests the sample size for UK survivors is around 230, through all cause mortality. The IQCODE score is subjective, as it comes from an 'informant' questionnaire, but the questionnaire has been validated and should not bias between-group comparisons. We would expect some loss of response rate from survivors, but could reasonably expect this loss to be similar in both groups. Results from the IQCODE scores will add to and complement dementia data from data linkage with National electronic health records. Additionally the IQCODE will prove a useful measurement of current cognition in this previously randomised cohort.

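### IQCODE completion depends on cognition through the consent and capacity rules, and the expectation of similar loss in both arms does not repair this

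*Protocol*

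**What the plan says.** **Purpose.** Section 3 justifies this phase on the ground that, for the linked records, "it is likely that these datasets under ascertain dementia". Section 9.3 makes the IQCODE a supplement to linkage for the main outcomes, which are compared by allocated arm with Cox and Kaplan-Meier methods.

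**Who can be assessed.** Inclusion criterion 4 in section 6.2 requires the participant's own consent and a nominated informant. Section 7.3 presumes capacity from the returned form, checks it again in the telephone call to the informant, and adds: "If there is any doubt over capacity we would not proceed with the questionnaire follow-up". It also acknowledges: "Some participants will not, for whatever reason, be able to consent or name an informant". Most of these are expected not to reply, and section 7.1 states: "For non-responders to both mailings we will not follow-up further". Their names leave the IQCODE database, "although their data would be kept for the followup into electronic health records".

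**Fallback.** If a relative happens to get in touch, section 7.3 says "the coordinator may ask for and record any dementia, type (if known) and date of diagnosis".

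**Loss.** Section 9.1 expects some non-response from survivors but says the study "could reasonably expect this loss to be similar in both groups". It gives no rate and no reason.

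**The concern.** The IQCODE is there to find dementia that linkage misses. The people most likely to have it are also the least likely to sign a form, name an informant or pass a capacity check. The check is made through the same informant who would supply the score, so an account of serious impairment can end the call in which impairment was to be measured.

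Missingness is then related to the outcome. Balance in total loss is a statement about numbers of forms and says nothing about which survivors are missing within each arm. If the hypothesis in section 3 is true, and surgery lowers cognitive decline, cognition-related loss would itself differ by arm. At stake are the number of additional cases the IQCODE can contribute, the absolute rates and differences it shows, and its precision.

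**Working it through.** There is no design calculation to reproduce. The protocol gives no error rate, power, effect size, event rate or response rate. The figure of about 230 is a count of survivors: 230/1069 = 21.5% of UK participants (section 7.1), or 230/1601 = 14.4% of the linked UK and Swedish cohort.

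The illustrations below use 230 split equally (115 per arm, following the 1:1 allocation in section 7.5, with equal survival assumed). **Every prevalence and completion rate is an assumption.**

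Let p be the true prevalence in an arm, r1 completion among cases and r0 completion among others.
- Completion in the arm = p·r1 + (1−p)·r0
- Observed prevalence = p·r1 / [p·r1 + (1−p)·r0]

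**A. Equal case completion by arm** (p = 0.20 deferred, 0.14 immediate; r1 = 0.30; r0 = 0.65)
- Deferred: 0.060/(0.060 + 0.520) = 0.060/0.580 = 10.3%; loss 42.0%.
- Immediate: 0.042/(0.042 + 0.559) = 0.042/0.601 = 7.0%; loss 39.9%.
- Cases seen: 115 × (0.20 + 0.14) × 0.30 = 11.7 of 39.1.
- Difference: 3.4 points against a true 6.0.
- Risk ratio: 0.68 against 0.70. Odds ratio: (0.042/0.559)/(0.060/0.520) = 0.65, equal to the true (0.14/0.86)/(0.20/0.80) = 0.65.

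**B. Unequal case completion by arm** (same p and r0; true risk ratio 0.70)

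| Case completion, deferred / immediate | Observed, deferred | Observed, immediate | Risk ratio | Total loss, deferred / immediate |
|---|---|---|---|---|
| 25% / 35% | 0.050/0.570 = 8.8% | 0.049/0.608 = 8.1% | 0.92 | 43.0% / 39.2% |
| 35% / 25% | 0.070/0.590 = 11.9% | 0.035/0.594 = 5.9% | 0.50 | 41.0% / 40.6% |

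In the second row total loss is almost identical by arm and the ratio is still well off.

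**C. Other prevalences** (30% deferred, 20% immediate; r0 = 0.70; 57.5 true cases; power for a two-sided 5% comparison of two proportions)

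| r1 | Cases seen | Completion, immediate / deferred | Observed, immediate / deferred | Difference | Risk ratio | Power |
|---|---|---|---|---|---|---|
| 70% | 40.2 | 70.0% / 70.0% | 20.0% / 30.0% | 10.0 points | 0.67 | 31% |
| 35% | 20.1 | 63.0% / 59.5% | 11.1% / 17.6% | 6.5 points | 0.63 | 20% |
| 14% | 8.1 | 58.8% / 53.2% | 4.8% / 7.9% | 3.1 points | 0.60 | 11% |

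**D. No true effect** (20% in both arms; r0 = 0.70). Completion is equal by arm throughout, yet cases seen fall from 32.2 to 16.1 to 6.4 of 46 as r1 goes from 70% to 35% to 14%.

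Cases, absolute differences and power are lost under every setting with r1 below r0 and a true effect. The ratio moves little unless case completion differs by arm, and then its direction depends on which arm loses more cases.

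**The case against.** The strongest reply is that these calculations describe a stand-alone IQCODE comparison, which is not the main analysis. That stands. The main outcomes combine linkage and IQCODE, and linked data are kept for those who cannot consent. No effect on the Cox analysis has been computed, and the documents do not allow one.

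Several stronger readings are tempting and are not supported:

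- *People with dementia are removed from the study.* They may be lost to the IQCODE only, and impaired people who keep capacity can take part.
- *The capacity rule contradicts the absence of exclusion criteria in section 6.2.* Inclusion criterion 4 already requires consent, so it largely covers this. Only a stop after a returned form sits awkwardly with the list.
- *Reasons for non-completion are destroyed.* The sentence "They would then be removed from the follow-up IQCODE study database" in section 7.1 concerns people who actively decline. For those unable to consent, section 7.3 speaks of removing the name. Neither says that allocation, linked status or a reason is erased; the protocol simply does not say that a reason is kept.
- *The treatment ratio is biased towards the null.* With equal case completion it barely moves. The value of 0.92 needs an added assumption, and reversing that assumption gives 0.50.

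It can also be said that the assumed losses of 42.0% and 39.9% are indeed similar, as section 9.1 expects. That is true, and it shows why the expectation gives no protection. The relative's report is a real mitigation, but it is passive, optional and limited to known diagnoses. Weighting and sensitivity analyses may properly sit in a statistical analysis plan, but what is recorded at mailing and on the telephone is fixed by the protocol.

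**Conclusion.** The point holds as a weakness in ascertainment. The protocol makes IQCODE completion depend on cognition, provides no active fallback, and answers only with an expectation about total loss. The likely harms are lost cases, understated absolute rates and differences, and lost precision. In the illustrations, halving completion among cases halves the cases seen. Any bias in the ratio depends on completion among cases by arm, which is unknown, and could go either way.

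The logic rests on the protocol's text. The sizes rest wholly on assumed prevalences and completion rates. Because linkage continues and the IQCODE can reach at most about 230 people, this does not undermine the main analysis as a whole. It should be fixed, and before the mailing, because reasons and reports not collected then are hard to recover.

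**What to change.** Leave the capacity rule unchanged.

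1. Keep every invited survivor in the analysis file under study number, with arm, linked dementia status and a reason code: completed, declined, no reply, capacity, died. Contact details can still be deleted as planned.
2. Make the already permitted record of dementia, type and date systematic. Ask for it at every capacity stop and at every contact from a relative. Subject to ethics and CAG approval, add one line for a relative or carer to the reply slip and the reminder.
3. Replace the assurance of similar loss in section 9.1 with a commitment to report completion by arm and by linked dementia status.
4. Count a capacity stop as impaired only in a sensitivity analysis. Stroke can also remove capacity, and section 3 cites fewer strokes after surgery, so making this the primary rule could favour surgery. It would also reach only those who returned a form.

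The cost is a small ethics and CAG amendment, one extra data field and a little more data entry. Nobody without capacity would be assessed.
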